Comparative Effects of Blood Flow Restriction and Traditional Strength Training on Proximal Shoulder Musculature: A Randomized Clinical Trial

Approved by the ethics committee of Instituto Politécnico de Saúde do Norte (31/CE-IPSN/2024).

April 2024

STUDY OBJECTIVES

This study compared a 4-week blood-flow-restriction (BFR) resistance-training program performed at 30% of one-repetition maximum (1RM) with traditional high-load strength training at 70% of 1RM on shoulder muscle strength, power, endurance, and hypertrophy in healthy adults.

STUDY DESIGN

Parallel-group randomized controlled trial with two intervention arms: an experimental BFR group ($n = 12$; 3 men, 9 women) and an active comparator high-load group ($n = 11$; 3 men, 8 women; one dropout). All participants provided written informed consent in accordance with the Declaration of Helsinki.

PARTICIPANTS AND RECRUITMENT

Healthy volunteers were recruited via social media, discussion groups, and physical postings at CESPU facilities. Individuals of both sexes were eligible because prior work indicates comparable metabolic responses to BFR across genders. Eligibility was screened using an online questionnaire covering demographics, sport participation, and medical history. Eligible respondents were contacted by email to schedule baseline testing.

Eligibility Criteria

Inclusion criteria

- Age 18–40 years
- Body mass index (BMI) 18.5–30 kg/m² (individuals with obesity are commonly excluded due to higher cardiovascular, respiratory, and rheumatologic risk)

Exclusion criteria

- Participation in sports that heavily use the dominant arm (e.g., tennis, volleyball, handball)
- Current upper-limb strength training
- History of trauma or surgery involving the dominant upper limb

- Acute or chronic shoulder pain or radiating pain
- Cervical disc herniation or prior cervical surgery
- Upper-limb edema
- History of deep-vein thrombosis or oncologic/metabolic disease
- Pregnancy
- Persistent symptoms during training: numbness, tingling, or pain >7/10 on a numeric rating scale (BFR group criterion)
- Missing more than one training session

Randomization was performed with Sealed Envelope™.

METHODS

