Analyses were performed in SPSS version 29.0 (SPSS Inc., Chicago, IL, USA). Quantitative variables are presented as mean \pm SD or median (interquartile range), as appropriate. Between-group comparisons used Fisher's exact test, the Mann-Whitney U test, or independent-samples t tests. Within-group pre- to post-changes were evaluated with paired-samples t tests. For significant outcomes, Cohen's d was calculated and interpreted as: very small, $0.01 < d \leq 0.20$; small, $0.20 < d \leq 0.50$; moderate, $0.50 < d \leq 0.80$; large, $0.80 < d \leq 1.20$; very large, $1.20 < d \leq 2.00$; and huge, $d > 2.00$. Statistical significance was set at $p < 0.05$.

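### Cohen's d is reported only for significant outcomes, with no named standardiser or small-sample correction, so reported effects are selected upward and their band labels may not be comparable

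*Combined protocol and SAP*

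**What the plan says.** The Statistical Analysis section of the combined protocol and SAP names two kinds of test on quantitative outcomes. "Within-group pre- to post-changes were evaluated with paired-samples t tests", and between-group comparisons use Fisher's exact test, "the Mann-Whitney U test, or independent-samples t tests". One effect-size rule then follows for everything: "For significant outcomes", Cohen's "d was calculated and interpreted as: very small", continuing with "small, $0.20 < d \leq 0.50$; moderate, $0.50 < d \leq 0.80" and "large, $0.80 < d \leq 1.20$; very large, $1.20 < d \leq 2.00$; and huge, $d > 2.00". The threshold is given as "Statistical significance was set at $p < 0.05", without sidedness.

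The section does not state:

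- which SD is the divisor for a paired or a between-group d;
- whether the between-group tests compare M1 scores or M0-to-M1 changes;
- any small-sample correction or confidence interval for d;
- what takes the place of d after a Mann-Whitney or Fisher test.

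The Study Design section gives "an experimental BFR group ($n = 12$; 3 men, 9 women" and a high-load group of 11 (3 men, 8 women) with one dropout.

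**The concern.** Two separate problems arise.

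First, d is computed only after a significance test has been passed. In arms of this size, a result that passes must have a sizeable observed d. A reader then sees only favourable labels. For a comparison that did not reach significance, the reader gets no effect size and no interval, although the comparison of two active programmes in 23 people is where the range of compatible effects matters most.

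Second, Cohen's d after a paired t test has more than one usual definition. Dividing by the SD of the changes and dividing by a raw-score SD give different values for the same physical gain. Reading either of them, and a between-group d, against one set of bands is meaningful only if the divisor is fixed and shared. As written, the divisor can be chosen after the data are seen.

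**Working it through.** The documents give no effect size, SD or correlation, so there is no stated figure to reproduce.

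**Inputs.** n = 12 and n = 11 (Study Design); 0.05 level and band limits (Statistical Analysis). Assumed: two-sided tests, a pooled-variance t test between arms, all 23 participants measured on each outcome, equal SDs at M0 and M1, and a pre-post correlation r between 0.3 and 0.95.

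**Step 1: smallest d that can be reported.**

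- Between arms, d divided by the pooled SD of the variable tested: t(0.975; 21 df) × sqrt(1/12 + 1/11) = 2.080 × 0.4174 = 0.868. This is in the large band.
- Paired, d divided by the SD of change: t(0.975)/sqrt(n) = 2.201/3.464 = 0.635 for n = 12, and 2.228/3.317 = 0.672 for n = 11. Both are in the moderate band.

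**Step 2: size of the upward selection.** Simulation with 200,000 trials per setting, normal data, and d averaged over significant trials only:

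| Comparison | True d | Significant | Mean d if significant |
|---|---|---|---|
| Between arms (12 v 11) | 0.5 | 21% | 1.14 |
| Between arms (12 v 11) | 0.8 | 45% | 1.23 |
| Paired, SD of change (n = 12) | 0.5 | 35% | 0.90 |
| Paired, SD of change (n = 12) | 0.8 | 71% | 1.03 |

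**Step 3: effect of the divisor.** With equal SDs, SD(change) = SD × sqrt(2(1 − r)), so change-SD d divided by raw-SD d is 1/sqrt(2(1 − r)):

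| r | Ratio | Raw-SD d of 0.60 (moderate) becomes |
|---|---|---|
| 0.3 | 0.85 | 0.51, moderate |
| 0.5 | 1.00 | 0.60, moderate |
| 0.7 | 1.29 | 0.77, moderate |
| 0.8 | 1.58 | 0.95, large |
| 0.9 | 2.24 | 1.34, very large |

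At r = 0.8, significant paired results are mostly one band higher than on the raw scale. At r = 0.9, all are one or two bands higher. At the extreme of r = 0.95 (ratio 3.16), some move three bands. Below 0.5 the shift reverses: at r = 0.3, a raw-SD d of 0.90 (large) becomes 0.90 × 0.845 = 0.76 (moderate).

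**Step 4: small-sample bias.** The Hedges factor J is 0.964 for 21 df, 0.930 for 11 df and 0.923 for 10 df. Uncorrected d is therefore about 4% too large between arms and 7-8% too large within arms if the within-arm SD of change is the divisor. Alone, this changes a label only just above a limit. For example, a paired d between 0.80 and 0.86 (n = 12) falls from large to moderate.

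**The case against.** The strongest reply is that the plan is silent rather than wrong. It does not say that the paired d uses the SD of change, and if the between-group tests compare changes, both values of d naturally rest on an SD of change. The mismatch in Step 3 then largely disappears. This stands. A reader might infer that the within-arm labels will be one or two bands too high. The documents do not support that as a fact, because it needs a particular divisor that the plan neither states nor excludes, and an r of about 0.8 to 0.9 that the plan does not give.

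A reader might also infer from Step 1 that the two lowest bands can never appear. That is too strong. On a raw-score SD, the smallest significant paired d at n = 12 is 0.635 × sqrt(2(1 − r)), which is 0.40 at r = 0.8 and 0.28 at r = 0.9, both in the small band. The 0.87 bound likewise applies only when d uses the SD of the variable tested by a t test. It does not apply to Mann-Whitney results.

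It is also fair to say that a change-SD and a raw-SD effect size are both legitimate if labelled, and that the pooled M0 SD is partly a preference. Each arm mixes 3 men with 8 or 9 women, so that SD would include any difference between the sexes in strength or throwing distance. Finally, a within-arm change and a between-arm contrast answer different questions, so a smaller between-arm d is to be expected even on a common scale.

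None of this answers the first problem. The restriction of d to significant outcomes is written in the plan, and its selective effect does not depend on r.

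**Conclusion.** The point holds in two parts of unequal certainty.

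The firm part is the significance filter. Under two-sided testing with 12 and 11 per arm, a t-test d between arms appears only from about 0.87, and a change-SD paired d only from about 0.64 or 0.67. Reported effects are selected upward, and non-significant comparisons get no effect size.

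The conditional part is the scale. If a change-SD paired d stands beside a raw-SD between-group d, the ratio is 1.00 at r = 0.5, 1.58 at 0.8 and 2.24 at 0.9. Labels can then be up to two bands too high over that range, or too low when r is below 0.5. The missing correction is minor.

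The matter concerns description and interpretation. No p-value, test decision or estimate in original units changes, so this is a change the plan should make rather than a flaw that invalidates the analysis.

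**What to change.** Replace the effect-size sentence in the Statistical Analysis section with a rule that does the following:

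1. Reports an effect size with a 95% CI for all four outcomes (arm circumference, shot-put distance, vertical lift strength, endurance time), within and between arms, whether or not p < 0.05.
2. Names the standardiser and uses the same one for both comparisons. The pooled M0 SD of each outcome is one suitable choice.
3. Applies the Hedges correction with the degrees of freedom of that SD. If the M0 SD is pooled over both arms (21 df), the correction is about 4% throughout. The 7-8% applies to a within-arm SD of change.
4. Applies the bands only to this value, and says whether the between-group comparison uses M1 scores or changes.

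The cost is a few lines of text and some recomputation from M0 and M1 data already collected. The downside is that some labels become less favourable.
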